Aim 1: Examine how medical cannabis use affects self-reported pain. H1: The effect of medical cannabis use on self-reported pain-severity will differ by THC/CBD content. The primary outcome will be change in BPI pain severity scale (ordinal variable, 0-10; measured at baseline and weekly for 14 weeks). A clinically significant change is 30% reduction in BPI pain severity scale.⁹² Secondary measures will include BPI pain interference scale and neuropathic pain (painDETECT). We will compare the proportion of participants who achieve clinically significant change in pain at 14 weeks between those who use high THC soft gel capsules and those who use high CBD soft gel capsules. BPI pain interference scale and painDETECT will be compared between those using high THC vs high CBD as well. We will use mixed-effects logistic regression to test the effect of study arm on pain relief across the course of the study. Results will be adjusted for covariates associated with the outcomes of interest on bivariate testing. We will repeat this model using alternative measures of medical cannabis (cumulative dose of THC and CBD).

Aim 2: Examine how medical cannabis use affects pro- and anti-inflammatory cytokines. H2: Medical cannabis that has higher THC content will have greater reduction in pro-inflammatory

cytokines ($TNF\alpha$, $IL-6$). *H3: Medical cannabis that has higher CBD content will have greater increase in anti-inflammatory cytokines ($IL-4$, $IL-10$).* We will examine how pro- and anti-inflammatory cytokines measured at 0 and 14 weeks change in participants using high THC products versus high CBD products. We will use mixed-effects linear regression analyses to examine intervention and time effects as well as intervention-by-time interactions. This approach is appropriate in the event that the pro- and anti-inflammatory cytokine data show a non-normal distribution. We will repeat this model using alternative measures of medical cannabis (cumulative dose of THC and CBD). We will adjust for other chronic conditions that may lead to change in inflammatory cytokines, such as obesity, cardiovascular disease, and diabetes.

Aim 3: Examine how medical cannabis use affects adverse events. *H4: Participants who use high THC (vs. high CBD) cannabis products will have more psychological symptoms, poorer ARV adherence, and less suppressed VL.* We will examine whether participants using high THC products vs high CBD products have a greater chance of adverse events, including psychological symptoms, ARV adherence, and VL. We will use mixed-effects linear regression analysis for continuous measures (VL, ARV adherence, and psychological symptoms). Each adverse event (Table 8) will be included in a separate model. We will repeat this model using alternative measures of medical cannabis (cumulative dose of THC and CBD).

Aim 4: Explore mechanisms by which medical cannabis promotes analgesia. *H5: Different doses of THC and CBD will have differing effects on inflammatory cytokines, psychological symptoms, and ultimately analgesia.*

We will use a pooled analysis of THC and CBD, using weekly questionnaires and PMP records. We will examine these relationships longitudinally in a stepwise process. First, we will conduct a mixed-effects model to examine how potential mediators lead to analgesia (reduction in BPI severity score). We will repeat analyses for possible mediators, including inflammatory cytokines and psychological symptoms. We will also determine if exposures influence changes in these variables over time, which in turn, influence change in analgesia (e.g., using time-lagged mediators and outcomes). Mediators found to be significant will be included in the final model.⁹² We will calculate the standardized total effect from the exposures to analgesia as well as the standardized mediational (i.e., indirect) effects via mediators. The mediational effect is calculated as the product of the effect from the exposures to the mediators, and the effect from the mediators to the outcome.

8) Data quality control and database management

Data management: Questionnaire, medical records, and PMP data will be de-identified and entered by study staff into a password-protected computer and database. Paper records will be stored in a locked filing cabinet that only research staff can access. Medical and PMP record data will be de-identified and entered in a secure HIPAA compliant web-based system. To protect confidentiality, we will use separate processes for ID- and name-based files and seek a certificate of confidentiality.

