The benefits of cannabis may be offset by its adverse events.²⁷ Cannabis is linked to psychological symptoms including anxiety, depression,²⁸ and psychotic symptoms.²⁹ In some studies, cannabis use is associated with poor ARV adherence and virologic failure;³⁰ in others, this is not the case.³¹ No studies have examined how THC/CBD content contributes to adverse events (psychological symptoms, poor ARV adherence, and virologic failure).

Our overarching goal is to test how medical cannabis use affects neuropathic pain, with particular attention to THC/CBD content and adverse events. We propose an observational cohort study of 100 PLWH with (a) neuropathic pain, (b) active certification for medical cannabis, and (c) intent of being dispensed soft-gel capsule products at a medical cannabis dispensary (including high THC: low CBD product and high CBD:low THC product). Over 14 weeks, participants will have 2 in-person visits and 15 phone-based questionnaires (one at baseline, and every week for 14 weeks). Data sources will be blood and urine samples, questionnaires, and medical and pharmacy records. The primary independent variable will be the type of soft-gel capsule product. The secondary independent variable will be reported cumulative THC and CBD dose. The primary outcome will be self-reported pain severity.³² Secondary outcomes will be pro-inflammatory cytokines (TNF α , IL-6), anti-inflammatory cytokines (IL-4, IL-10),¹⁵ psychological symptoms (symptoms of depression,³³ anxiety,³⁴ and psychosis³⁵), ARV adherence, and VL. Among PLWH with neuropathic pain, we will:

Aim 1: Examine how medical cannabis use affects self-reported pain. *H1:* The effect of medical cannabis use on self-reported pain-severity will differ by THC/CBD content.

Aim 2: Examine how medical cannabis use affects pro- and anti-inflammatory cytokines.

H2: Medical cannabis that has higher THC content will have greater reduction in pro-inflammatory cytokines (TNF α , IL-6). *H3:* Medical cannabis that has higher CBD content will have greater increase in anti-inflammatory cytokines (IL-4, IL-10).

Aim 3: Examine how medical cannabis use affects adverse events. *H4:* Participants who use high THC (vs. high CBD) cannabis products will have more psychological symptoms, poorer ARV adherence, and less suppressed VL.

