Aim 4: Explore mechanisms by which medical cannabis promotes analgesia. Using a pooled analysis of reported cumulative THC and CBD dose we will explore how THC/CBD content, inflammatory cytokines and psychological symptoms relate to cannabis and analgesia. *H5:* Different doses of THC and CBD will have differing effects on inflammatory cytokines, psychological symptoms, and ultimately analgesia.

Findings will provide key data that will be integral to the care of PLWH.

1.B. Significance

PLWH have a high burden of pain, especially neuropathic pain. Pain is prevalent in 39 to 85% of PLWH.¹⁻⁸ It is often due to neuropathy,^{9,10} which is a common complication of HIV infection and its treatment. Neuropathic pain occurs in up to 57% of ambulatory PLWH, of which the vast majority (40-90%) experience painful neuropathy.¹¹⁻¹³ It is associated with significant disability and poor HIV outcomes, including functional impairment, reduced quality of life, poor ARV adherence, virologic failure, and poor retention in care.¹⁴⁻¹⁸

The etiology of neuropathic pain in PLWH is complex. Neuropathic pain in PLWH was traditionally thought to be related to direct toxic effects from early ARV regimens.¹⁹ However, neuropathic pain remains prevalent despite phasing out of these ARVs.^{13,20} It is now understood that peripheral neurons experience inflammation indirectly through HIV-infected monocyte-macrophage lineage cells.¹⁹ Infected cells excrete pro-inflammatory cytokines (TNF α , IL-6)²¹ and down-regulate anti-inflammatory cytokines (IL-4 and IL-10), leading to astrocyte activation in the spinal dorsal horn.²²⁻²⁴ This pro-inflammatory state persists despite VL suppression, resulting in neuronal injury, peripheral nerve cell apoptosis, neurodegeneration, and pain.^{19,25}

Neuropathic pain, psychological symptoms and HIV are tightly interrelated. Psychological symptoms, including depression and anxiety, are commonly experienced by PLWH and are associated with neuropathic pain.²⁶ Further, symptoms of depression and anxiety are associated with increased pro-inflammatory (TNF α , IL-6) and decreased anti-inflammatory (IL-4, IL-10) cytokines.²⁷ [name] (Advisor) described the complex relationship of the biological, psychological, and social factors that lead to chronic pain in PLWH in the adapted Biopsychosocial framework (BPS) (Figure 1).²⁶

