Cannabis use may lead to worse HIV outcomes, but findings are mixed. Cannabis use is associated with improved, worsened, and no change in VL suppression.⁷¹⁻⁷³ Cannabis use is associated with improved, worsened, and no change in ARV adherence.^{72,74-81} In all of these studies, street cannabis use was examined rather than medical cannabis. *To our knowledge, no studies have examined how medical cannabis affects HIV outcomes. In the setting of rapidly increasing medical cannabis acceptance, it is critical to understand how cannabis affects HIV outcomes and psychological symptoms in PLWH.*

Summary: Neuropathic pain in PLWH is common and difficult to manage. Medical cannabis is an emerging new treatment, but gaps remain in our knowledge about its efficacy, mechanism, and effect on adverse events. To better understand how medical cannabis affects neuropathic pain in PLWH, we propose an observational cohort study to examine how medical cannabis affects pain, inflammation, and adverse events.

2) Study Design

2. A. Overview of study design: Our goal is to understand how medical cannabis affects self-reported pain, with attention to THC/CBD content, markers of inflammation, and adverse events. We will conduct an observational cohort study of 100 PLWH with neuropathic pain, active medical cannabis certification, and intent to use newly dispensed soft-gel capsule product from a medical cannabis dispensary. At baseline and over the following 14 weeks, participants will have 2 in-person visits and 14 web-based weekly questionnaires. Data sources will include questionnaires, medical

Table 4. Eligibility Criteria

Criterion	Source
Inclusion Criteria	
≥18 years old	SQ
Diagnosis of HIV	MR
Fluency in English	SQ
Active certification for medical cannabis	MR
No medical cannabis dispensed in 60 days or used within the previous 30 days	PR SQ
Intends to have new soft-gel capsule product dispensed at Vireo	MR PR
ICD-10 diagnosis code for neuropathic pain, OR Neuropathic pain in problem list of electronic medical record, OR Neuropathic pain per medical cannabis certification form, OR Neuropathic Pain Questionnaire- Short Form >0	MR MR MR SQ
Exclusion Criteria	
Inability to provide informed consent	SQ
Inability to complete 14 wks of study visits	SQ
Medical cannabis use within 30 days prior to enrollment	PR
Unique pain symptoms (e.g., multiple sclerosis, rheumatoid arthritis)	MR
Terminal illness	MR
Current or prior psychotic disorder	SQ

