Unregulated cannabis, opioid, cocaine, or benzodiazepine use in the past 30 d	SQ, U

records, pharmacy records, and blood and urine samples (see Table 8). Our primary independent variable will be the initial soft-gel product obtained

from the medical cannabis dispensary, and our primary outcome will be self-reported pain severity using the Brief Pain Inventory severity subscale.

2.A. Settings: Montefiore Health System (Montefiore) is the largest healthcare system in the Bronx, NY with 11 hospitals and over 200 community clinics. Directed by [name] (Primary Mentor), the Montefiore Medical Cannabis Program includes 2500 patients certified by 25 physicians; approximately 25% of patients are PLWH. Vireo is a medical cannabis company with dispensaries in 11 states; two dispensaries are located in the NYC area. As of August 2020, in NY, Vireo served over 30,000 unique patients. Vireo staff will refer potential participants to the study and facilitate study retention; recruitment will occur at dispensaries.

2.C. Research visits and data collection.

Eligibility criteria. *Inclusion criteria* are: 1) ≥ 18 years old; 2) diagnosis of HIV 3) fluency in English; 4) actively certified for medical cannabis (medical records); 5) no medical cannabis dispensed in 60 days or used within the previous 30 days; 6) intent to have new soft-gel capsule product dispensed at Vireo (PMP or medical record); 7) ICD-10 diagnosis code for neuropathic pain, OR neuropathic pain in problem list of electronic medical record, OR neuropathic pain per medical cannabis certification form, OR Neuropathic Pain Questionnaire Short Form >0 .

Exclusion criteria are: 1) inability to provide informed consent; 2) inability to complete 14 weeks of study visit; 3) medical cannabis use within 30 days prior to enrollment; 4) unique pain symptoms (e.g. multiple sclerosis, rheumatoid arthritis); 5) terminal illness; 6) current or prior psychotic disorder; 7) unregulated cannabis, opioid, cocaine, or benzodiazepine use in the past 30 days (self-report and urine drug screen); 8) dispensed opioids or benzodiazepines within 60 days of enrollment; 9) non-steroidal anti-inflammatory (NSAID) use within 7 days prior to enrollment; 10) steroid use within the past 14 days with duration of therapy >21 days; 11) COVID vaccination within 14 days of screening.

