Medical record data will be extracted 6 months prior to enrollment through 14 weeks after enrollment, including medical cannabis certification forms, prescriptions, and notes regarding pain treatment (nerve blocks, physical therapy, occupational therapy).

Pharmacy and PMP records will be extracted for medications dispensed 6 months prior to enrollment to 14 weeks after enrollment. Data will include ARVs, controlled substances (e.g., dispensed medical cannabis products, THC and CBD content in milligrams, doses dispensed) and pain medications (i.e., anticonvulsant, selective serotonin reuptake inhibitor, topical lidocaine).

Blood draws: Approximately 15 ml of blood will be drawn to assess VL, CD4 count, pro-inflammatory and anti-inflammatory cytokines. *VL and CD4 count* will be processed through Montefiore's central lab. VL will be quantified using the Abbott RealTime HIV-1 Viral Load assay (Abbott Park, Illinois), and CD4 count will be measured by the BD Multitest (BD Biosciences, San Jose). *Pro- (TNF α , IL-6) and anti- (IL-4, IL-10) inflammatory cytokines* will be analyzed using the Olink cytokine assay (Thermo Fisher Scientific, Waltham, MA) at Mount Sinai's Human Immune Monitoring Center.

Urine samples: We will check urine drug screens to confirm that patients are taking medical cannabis and to confirm that they abstain from opioid use during the course of the study.

4) Recruitment

4.A. Recruitment will occur from Montefiore's Medical Cannabis Program in which 25 patients are certified per month. Of those, approximately 6 are PLWH. In June 2020, [name] expanded the program to include Montefiore's HIV clinic, where 2500 PLWH receive care. With this expansion, at least 20 PLWH per month are certified for medical cannabis, and an overwhelming majority have pain. We will also leverage the clinical core of the ERC-CFAR to identify and recruit PLWH with neuropathic pain. Through these targeted clinical activities, we anticipate that enrolling 100 PLWH over 36 months (3-4/month) will be feasible.

Participant tracking: To facilitate tracking participants over 14-weeks, we will record: 1) participants' address and phone numbers; 2) contact information of family or friends; and 3) locations where participants work. This method allowed for 85% retention over 6 months of follow up in previous research studies.⁸⁵⁻⁸⁷

4.B. Participant retention

We will use previously established methods by my mentors to maximize retention in clinical trials.

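### Eligibility asks only for an HIV diagnosis and Aims 2-3 name no antiretroviral variable, so people off or newly starting ARVs may enter the adherence, viral load and cytokine models with no rule for handling them.

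*Combined protocol and SAP*

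**What the plan says.** Section 2.C lists 7 inclusion and 11 exclusion criteria. The HIV criterion is "2) diagnosis of HIV 3) fluency in English", and Table 4 has the same ("Diagnosis of HIV", checked in the medical record). Nothing refers to ARV use, time on ARVs, a recent start, or suppression at baseline. The list does screen out other influences on inflammation: recent NSAID use, and also "10) steroid use within the past 14 days with duration of therapy >21 days; 11) COVID vaccination within 14 days of screening".

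The outcomes most exposed to ARV status are secondary. Under H4, high-THC users "will have more psychological symptoms, poorer ARV adherence, and less suppressed VL". H2 and H3 concern cytokines, which section 1.B links to HIV itself ("Infected cells excrete pro-inflammatory cytokines"). VL and cytokines are measured at weeks 0 and 14.

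Section 7.A has four adjustment rules, and none names ARV status:
- The general rule covers age, sex and comorbidities, and applies only if these differ between arms.
- Selection of covariates by bivariate testing appears under Aim 1 only.
- For Aim 2: "We will adjust for other chronic conditions that may lead to change in inflammatory cytokines, such as obesity, cardiovascular disease, and diabetes".
- For Aim 3, a mixed-effects linear model is given for each outcome, with no covariates.

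Missing data are to be multiply imputed. The information needed is nevertheless collected. Section 3.C states "Pharmacy and PMP records will be extracted for medications dispensed 6 months prior to enrollment to 14 weeks after enrollment", ARVs are among the items extracted, and VL is measured at week 0.

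**The concern.** Two kinds of participant can meet every criterion and still distort the Aim 2-3 models.

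The first is a person with no ARVs prescribed. Adherence is undefined for that person, and the plan does not say how to score it. Entered as zero, it records the absence of a prescription as total non-adherence. Left missing, it falls under the imputation rule, which would create adherence values for treatment that was never taken. Neither figure bears on H4, and this problem does not depend on any imbalance between products.

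The second is a person who starts or restarts ARVs around enrolment. Their VL would be expected to change between weeks 0 and 14 whichever capsule they use. If starters are equally common in both product groups, this adds noise. If they are not, it biases the contrast, and a self-selected comparison of about 42 per arm does nothing to prevent that.

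The protocol's own background makes ARV interruptions foreseeable: it associates neuropathic pain with poor ARV adherence, virologic failure and poor retention in care, and the cohort is selected for that pain.

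**Working it through.** **Inputs from the documents.** Section 3.A gives 50 per arm with 15% attrition, hence 42 per arm, and a target effect of d = 0.5 with ICC 0.4 and power above 90% for Aims 2-3. The share of participants off or starting ARVs, and the size of their VL change, are not given. Every such value below is an assumption.

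**The plan's own power figure.** With 14 repeated measures, the effective n per arm is 42 × 14 / (1 + 13 × 0.4) = 588 / 6.2 = 94.8. Power for d = 0.5 is then 0.93, so the stated figure reproduces on that reading. With one value per participant and 42 per arm, power is 0.63. The second reading is closer to outcomes measured only at weeks 0 and 14.

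**Adherence.** No formula is needed to show the gap, because the quantity does not exist for someone with no ARVs prescribed. If such a person were scored 0 on a 100-point scale where an assumed 95 is typical, one person would move an arm mean by 95 / 42 = 2.3 points. This applies only under zero scoring, which the plan neither states nor rules out.

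**VL, shift in one arm.** Assume k starters of 42 in one arm and none in the other, each falling from 100,000 to 50 copies/mL. That is log10(100,000 / 50) = 3.30. The shift in that arm's mean is k × 3.30 / 42:

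| k | Shift (log10) |
|---|---|
| 1 | 0.08 |
| 3 | 0.24 |
| 5 | 0.39 |

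**VL, could the shift pass for a product effect?** Suppose nobody else changes. The two-sample t statistic for k versus 0 is √(41k / (42 − k)), on 82 degrees of freedom. The size of the fall cancels out.

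| k versus 0 | t | p |
|---|---|---|
| 1 | 1.00 | 0.32 |
| 3 | 1.78 | 0.08 |
| 4 | 2.08 | 0.04 |
| 5 | 2.35 | 0.02 |

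Starters inflate the standard error as well as the mean, so it takes a 4-versus-0 split to reach nominal significance. Ordinary variation in the other participants would generally weaken this further.

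**Bias in SD units.** An excess of k starters with a change of D SD biases the contrast by (k / 42) × D. With k = 3 and D = 2 this is 0.14 SD; with k = 5 and D = 3 it is 0.36 SD. The target effect is 0.5 SD.

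**Noise when the arms are balanced.** If a fraction f in both arms has a change of D SD, the outcome SD is multiplied by √(1 + f(1 − f)D²).

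| f, D | SD multiplier | Power, effective n 94.8 | Power, 42 per arm |
|---|---|---|---|
| 0 | 1.00 | 0.93 | 0.63 |
| 5%, 2 | √1.19 = 1.09 | 0.88 | 0.56 |
| 10%, 3 | √1.81 = 1.35 | 0.73 | 0.40 |

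**The case against.** The case for leaving the plan alone has several parts. Broad eligibility is a legitimate choice for an observational cohort. Recruitment draws largely on people already in care, including an HIV clinic. Only secondary outcomes are touched. The documents give no reason why starting ARVs should track capsule choice. All of this stands. It argues against changing eligibility, but it supplies neither a rule for adherence in people not on ARVs nor an ARV term in the models.

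A reader might infer more than the documents support:
- **That such people will enrol.** The criteria show only that they may. No share is given.
- **That a few starters would create a false product difference.** Bias needs imbalance, and 3 versus 0 does not reach nominal significance even with no other noise.
- **That TNFα and IL-6 would fall in starters.** The documents give no such effect or size, and section 1.B says the inflammatory state persists despite suppression. The list of Aim 2 covariates is also introduced as examples, so it is not strictly closed.
- **That people off ARVs fall outside the mechanism studied.** Section 1.A describes inflammation as present whatever the suppression status, which covers both suppressed and unsuppressed people.
- **That the Aim 2-3 analyses should be confined to people with uninterrupted ARV dispensing.** Dispensed ARVs are themselves an Aim 3 measure. That restriction would select on refill adherence and could remove the very people H4 concerns.

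**Conclusion.** The gap is real and limited to secondary outcomes. It is clearest for adherence: the analysis set is undefined, and either default handling produces a figure with no meaning for anyone without ARVs prescribed. One such person does not make the whole comparison uninterpretable, but the rule should exist before the data are analysed.

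For VL, starters certainly cost precision. They bias the product contrast only if unevenly split. On the assumptions shown, an excess of 3 to 5 of 42 in one arm is worth 0.14 to 0.36 SD. For cytokines, an ARV effect is plausible but cannot be sized from the documents.

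All magnitudes rest on assumed numbers of starters, assumed changes and, for bias, an assumed imbalance. The primary pain analysis is not in question.

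**What to change.** Amend section 7.A, using data already extracted:

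1. **Adherence.** Restrict the ARV-adherence analysis to participants with ARVs prescribed or dispensed at baseline. Define this by treatment status, not by complete refills, so that poor adherers stay in. Do not impute adherence for anyone else.
2. **VL and cytokines.** Keep all participants. Prespecify baseline ARV status (off, recently started, established), derived from the dispensing records, as a covariate together with its interaction with time. The main effect alone would not let starters follow their own course from week 0 to week 14. The sponsor should state the cut-off between recently started and established in advance.
3. **Sensitivity analysis.** Repeat the VL and cytokine models without participants who were off or newly starting ARVs at baseline. Flag and describe starts or restarts after baseline, but do not exclude on them: a restart may follow non-adherence, which is itself an outcome.

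Eligibility and Aim 1 stay as they are. The cost is one derived variable, a few extra model terms and slightly fewer participants in the adherence analysis.
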